### 7 Study Design and Plan

This study is a 'non-interventional study' as defined in: G-STND-PV-006, Directive 2001/83/EC (4) and will follow the guidelines for GPP (2). Additional applicable sponsor SOPs are: 1410A-SOP-0000001.03, DE-BE-MED-ALL-025.

#### This means that:

- The assignment of a patient to a particular therapeutic strategy is not decided in advance by the study protocol but falls within current practice
- No additional diagnostic or monitoring procedures shall be applied to the patients
- Epidemiological methods shall be used for the analysis of collected data

- Pre-rolled TachoSil® is prescribed in accordance with the terms of the marketing authorisation(s)
- The prescription of pre-rolled TachoSil® is clearly separated from the decision to include the patient in the study

### 7.1 Study Schedule

Planned Start of Study:

Planned collection of first data point:

October 2015

Planned collection of the last data point:

November 2016

Planned End of Study:

Planned completion of the Study Report:

May 2017

The Start of Study is defined as country specific IEC votes are available.

The End of study is defined as database lock.

Sponsor will ensure that End-of-Study notification is submitted to the concerned authorities and IEC for each site, for each country and for the complete study, as locally required.

Global Research will ensure that results are posted on "clinicaltrials.gov" and Sponsor will ensure that results are posted as required by local authorities.

Based on upcoming knowledge, Takeda might choose to terminate the study prematurely. In such case the Committee(s), study sites, IECs and authorities will be informed promptly.

## 7.2 Discussion of Study Design

This study is a non-interventional, international, prospective, multi-site cohort study in patients planned for laparoscopic surgery in the field of gynecology, urology or visceral surgery. A patient can be included in the study when the physician has decided to use pre-rolled TachoSil® according to the local SmPC.

There are no treatment groups or interventions to which the patients can be randomly assigned. Data will be collected in a routine setting. Participating physicians will not perform any medical procedures that are outside of their normal routine. All treatment decisions are at the sole discretion of the participating physicians and reflect their current standard of care. The decision to apply pre-rolled TachoSil® must be made independently from the decision to include a patient in this study.

Results from this study are prone to selection bias, e.g. by selecting sites experienced in using pre-rolled TachoSil® in laparoscopic surgery, or by including patients with known surgical outcome. Also confounding factors prevail in patients in a real-world setting, e.g. by indication, concurrent disease, concomitant drugs, or differing surgical procedures among sites.

It is acknowledged that such biases are present in any observational study. These limitations of the study design are inherent and result from the non-interventional character and the voluntary participation of physicians and patients.

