#### 6.3 Patient Information and Written Informed Consent

The Site Study Responsible must give the patient (and if applicable, legal guardian) oral and written information about the study in a form that the patient (legal guardian) can understand, and obtain the patient's (and if applicable, the patient's assent and the legal guardian's)

written consent before collection of identifiable patient information (hereinafter referred to as personal data). Before consenting, the patient (and if applicable, legal guardian) must be left with ample time to consider and to pose questions.

Since the study is observational the consent only concerns the data collection per se and is no consent to any experimental procedure or treatment.

As patients will only be eligible for study participation in case pre-rolled TachoSil® has been applied during surgery, information regarding the study will be provided to potential participants before the surgery, but consent will be collected only after the surgery.

The patient must agree that sponsor personnel, their representatives or IEC or CA personnel (national or other) may require direct access to the patient's data / personal records which were collected, processed and stored in an anonymized form.

The patient must agree that his / her data will be processed and stored in an anonymized form for evaluation of this study and any later overviews. Data may also be transferred in anonymized form to third parties, e.g. other companies or authorities, that may be located in other countries with potentially different regulations for data.

The patient and legal guardian, if applicable, has the right to withdraw his/her consent at any time without prejudice. In the Informed Consent Form it is stated that if consent is withdrawn, any data collected before withdrawal of consent will be kept unless its deletion is actively requested by the patient. The original, signed Informed Consent Forms must be kept on the Site.

For details, see the Patient Information Sheet and Informed Consent Form.

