# 7.3 Selection of Study Population

It is planned to include up to 105 Austrian and 360 German inpatients who have undergone laparoscopic surgery in the field of gynecology, urology and visceral surgery where prerolled TachoSil® was applied and who are 18 years or older.

Contraindications, such as hypersensitivity to the active pharmaceutical ingredient or to another ingredient of pre-rolled TachoSil®, are to be observed according to the current SmPC.

The observational period for individual patient will last from surgery (V0: Baseline) until date of discharge from hospital (V1: Final visit).

Data will be collected from patient files as well as study specific questions answered by the treating physician.

Written informed consent to use of collected data must always be obtained before collection of any study specific personal, sensitive data.

Subjects should be included in the study only once.

Data erroneously collected from subjects for which written consent is not available, will not be included in or will be deleted from the database.

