# 11.3 Determination of Sample Size

It is planned to collect data from up to 50 german hospitals and 10 ustrian hospitals performing laparoscopic surgery, from departments of gynecology, urology and visceral surgery. Each study centre should document only up to 20 patients.

As primary outcome measures the peri- and post-surgery assessment by the surgeon with respect to ease of use and overall satisfaction in the operation, using 5-point-Likert-Scales (1 = easy/satisfied, 5 = difficult/ not satisfied) are fixed in the study protocol. It is expected that

the use of pre-rolled TachoSil® is easier than the application of planar TachoSil® prepared/rolled by the surgeons themselves.

No published paper could be found with an identical outcome measure 'ease of use', which could have served as base for sample size calculation. Therefore the results of an older study with a specific MIS -applicator as a surrogate approach (Nycomed Arzneimittel GmbH 1998) were used.

Amongst others a parameter called 'Handhabungs-Score' (handling- score) was considered as outcome parameter according to the study protocol. This parameter comes very close to the parameter 'ease of use' intended to be used in the present RollOut-study. This score was calculated as the sum of the answers from a questionnaire with 5 AMISA-specific items. In the best case, this score takes a value of 5, in the worst case a value of 17. The results for the handling score showed that in 82% of cases the score was less or equal 9 points and about 18% greater than 9 points.

To show in a 1-group design (NIS) that this rate can be reduced with the use of pre-rolled TachoSil® significantly to 9%- points ( $\alpha$ = 0.05, power = 80%, two-tailed one group Chi²- test) it takes a minimum of 122 patients without any drop-out (see Table 2 below). To investigate this hypothesis in 3 fields of surgery (gynecology, urology and visceral surgery) independently, a total of 366 patients is needed. Since it is expected to improve the power from 80% up to 90% a minimum of 155 patients in each field and a total up to 465 should be included into the Study.

Test significance level, $\alpha$	0.050	0,050
1 or 2 sided test?	2	2
Null hypothesis proportion, $\pi_0$	0.180	0,180
Alternative proportion, $\pi_A$	0.090	0,090
Power (%)	80	90
N	122	155

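### Selection of patients with a known outcome is called inherent, but part of it is avoidable: no consecutive inclusion is required and eligible patients not enrolled are not counted

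*Protocol*

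**What the plan says.** Protocol section 7.2 gives two examples of selection bias: choosing sites experienced with the product, "or by including patients with known surgical outcome". It closes the subject with the statement "These limitations of the study design are inherent and result from the non-interventional character and the voluntary participation of physicians and patients".

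The rules that govern enrolment stand elsewhere:

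- **Protocol 6.3, consent.** "information regarding the study will be provided to potential participants before the surgery, but consent will be collected only after the surgery". The reason is given in the same sentence: "As patients will only be eligible for study participation in case pre-rolled TachoSil® has been applied during surgery".
- **Protocol 8, data collection overview.** Signed consent and the eligibility check are both marked in the interval from the end of surgery to discharge.
- **Protocol 7.3, observation period.** It also runs from surgery to discharge.
- **Protocol 7.2 and 7.4, inclusion.** Both say that a patient may be entered once the physician has decided to use the product. This is a permission, with no order of inclusion attached.
- **Protocol 9.3, adverse events.** Documentation starts only once consent has been given and the product applied.
- **Protocol 10.1 and 14, lists.** These mention a patient identification list and a list of participating patients. Neither covers patients who were eligible and not enrolled.
- **SAP 4.1.1 and 5.1.** The analysis is confined to eligible, consenting patients with all mandatory forms. No table of eligible against enrolled patients is foreseen.

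**The concern.** The protocol names a bias, attributes it to the type of study, and takes no step against it. Yet its own enrolment rules leave the route open. By the time anyone can be enrolled, the surgeon knows how the product handled, which is half of the primary outcome. If consent is taken late in the stay, bleeding, lymph leakage and most of the length of stay may be known as well. The site may then enrol the patient or not, and the study keeps no record of the choice.

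There is no control group in which such a shift would show. The stated purpose in protocol section 3 and SAP section 1.8 includes confirming advantages of the pre-rolled form in use. If poor cases are enrolled less often, the ratings and complication rates look better than they are, and without a denominator a reader cannot tell by how much.

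**Working it through.** **1. Is the bias inherent?** Protocol section 7 defines non-interventional by four features that matter here: treatment is not assigned by the protocol, no diagnostic or monitoring procedure is added, the product is used within its marketing authorisation, and the decision to use it is separate from the decision to include. Approaching every consecutive user and logging each use breaches none of these. Voluntary participation explains refusals and which sites join. It does not explain free choice among eligible patients within a site. Section 6.3 explains why consent follows surgery; it does not explain why it may wait until discharge, or why inclusion is optional.

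**2. The plan's own figures** (protocol 11.3: 18% against 9%, two-sided α = 0.05, one-group chi-square test).

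n = [z(0.975)·√(0.18×0.82) + z(power)·√(0.09×0.91)]² / (0.18 − 0.09)²

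- 80% power: 121.94, so 122.
- 90% power: 154.80, so 155; 3 × 155 = 465.

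Both reproduce the protocol.

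**3. Effect of selection.** The documents give no selection rate, so r is an assumption: patients with a poor outcome are enrolled at r times the rate of the others. With true rate p,

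observed rate = p·r / (p·r + 1 − p).

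*Handling.* Take p = 18%, the protocol's reference rate, so that the product has no effect. The observed rate equals 9% when r = (0.09×0.82)/(0.18×0.91) = 0.0738/0.1638 = 0.45. Check: 0.081/(0.081 + 0.82) = 9.0%. The last column is the exact binomial probability that the protocol's test at n = 155 declares an improvement.

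| r | Observed rate (true 18%) | Probability of a false improvement |
|---|---|---|
| 1.0 | 18.0% | 2.1% |
| 0.9 | 16.5% | 5.8% |
| 0.8 | 14.9% | 14.6% |
| 0.7 | 13.3% | 31.4% |
| 0.5 | 9.9% | 80.6% |

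*Complications.* The documents give no rate; 5% and 10% are assumed.

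| r | True 5% | True 10% |
|---|---|---|
| 0.9 | 0.045/0.995 = 4.5% | 0.09/0.99 = 9.1% |
| 0.5 | 0.025/0.975 = 2.6% | 0.05/0.95 = 5.3% |

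**4. What a log would allow.** If a fraction f of eligible patients is captured and 9% of them have a poor outcome, the rate among all eligible patients lies between 0.09f (no missed patient is poor) and 0.09f + (1 − f) (all are).

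- f = 0.90: 8.1% to 18.1%.
- f = 0.80: 7.2% to 27.2%.

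The upper bound stays at or below 18% only if f ≥ 0.82/0.91 = 90.1%. Without a log, f is unknown and no bound can be given.

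**The case against.** The strongest reply is that the protocol discloses exactly this bias, that the SAP (section 2.1) tests no hypothesis, and that some of the bias is unavoidable. All three points stand. Disclosure is not mitigation, however, and a descriptive rate is shifted by selection just as a tested one is. The false-improvement probabilities therefore illustrate the protocol's planned test, not the SAP's analysis.

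The monitoring plan mentioned in protocol section 10.1 is not available, so the absence of a log can be stated only for these two documents. Protocol section 11.1 also foresees listing events reported directly to the sponsor or authorities, so events in non-enrolled patients might surface there, but without a count of uses to set them against.

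A reader might infer four stronger things that the documents do not support:

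- **That consent has no time limit.** Section 8 sets one: discharge. The fault is that the interval is as long as the outcome period.
- **That the cap causes the selection.** Section 11.3 states "Each study centre should document only up to 20 patients", but planned averages are well below this: 465/60 = 7.75 per site (Germany 360/50 = 7.2, Austria 105/10 = 10.5) and 120/12 = 10 in the SAP. On average it does not bind, and it does no harm if patients are taken consecutively.
- **That every outcome is biased favourably.** This is assumed, not shown. Longer stays leave more time to obtain consent, which could push length of stay and complications the other way. Nor do the documents say that the rating surgeon always does the enrolling.
- **That a short consent window is the remedy.** It cannot protect the ease-of-use rating, since handling is known when surgery ends. It could exclude patients with complications or in intensive care, and it pulls against the ample time to consider that section 6.3 promises.

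**Conclusion.** The point holds in a limited form. Section 7.2 presents as wholly inherent a bias that is partly a consequence of permissive inclusion, a consent interval spanning the outcome period, and the lack of any count of eligible patients not enrolled. Consent after surgery is justified by the eligibility rule and is not itself the fault.

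The size is unknown. On assumed selection factors it ranges from small (5% shown as 4.5% at r = 0.9) to the whole planned effect (18% shown as 9% at r = 0.45). The handling illustration borrows the 18% from an older study's handling score for a different applicator; the documents define no cut-off on the present 5-point scale. Direction is also an assumption. What does not depend on these assumptions is that, without a denominator, neither size nor direction can be assessed. This should be changed, because the remedy is cheap and compatible with the design.

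**What to change.** - **Protocol 6.3 and 7.3.** Require each site to approach every consecutive eligible patient in whom pre-rolled TachoSil was used, until its quota is reached.
- **Site log.** Keep an anonymous log of all such uses: date, surgical field, enrolled yes or no, reason for non-inclusion. It should hold no identifiers, so that it stays outside the consent requirement for identifiable information in section 6.3.
- **SAP.** Report enrolled over eligible per site, and give worst-case bounds for the main rates as in step 4 of the working. For the bounds, the captured fraction should be patients analysed over patients eligible, since SAP section 5.1 drops those without all mandatory forms.
- **Protocol 7.2.** Reword to say that selection on known outcome is limited by the consecutive rule, and that refusals and inability to consent remain.

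The cost is a short protocol change, submitted to the ethics committees as section 6.1 requires for amendments, a one-page log, and a few minutes of site time per patient. Potential participants are already informed before surgery, so no new contact is needed. The sample size figures (122, 155 and 465) are unchanged. The rule limits the bias and makes it possible to bound; it does not remove it.

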# 7.3 Selection of Study Population

It is planned to include up to 105 Austrian and 360 German inpatients who have undergone laparoscopic surgery in the field of gynecology, urology and visceral surgery where prerolled TachoSil® was applied and who are 18 years or older.

Contraindications, such as hypersensitivity to the active pharmaceutical ingredient or to another ingredient of pre-rolled TachoSil®, are to be observed according to the current SmPC.

The observational period for individual patient will last from surgery (V0: Baseline) until date of discharge from hospital (V1: Final visit).

Data will be collected from patient files as well as study specific questions answered by the treating physician.

Written informed consent to use of collected data must always be obtained before collection of any study specific personal, sensitive data.

Subjects should be included in the study only once.

Data erroneously collected from subjects for which written consent is not available, will not be included in or will be deleted from the database.

#### 7.4 Treatments

Non-interventional/observation – no experimental treatments/pharmacotherapy are applicable.

A patient can be included in the study when the physician has decided to use pre-rolled TachoSil® according to the local SmPC.

There are no treatment groups or interventions to which the patients can be randomly assigned. Data will be collected in a routine setting. Participating physicians will not perform any medical procedures that are outside of their normal routine. All treatment decisions are

at the sole discretion of the participating physicians and reflect their current standard of care. The decision to apply pre-rolled TachoSil® must be made independently from the decision to include a patient in this study.

# 8 Conduct

Data collection overview:

Type of data point	Timing of data point			
	Before	At time of	Time interval 1	End of data
	diagnosis/	surgery	(After surgery	collection (day of
	treatment		until discharge	discharge from
			from hospital)	hospital)
Investigator contract	X			
signed	^			
ICF signed			х	
Inclusion/Exclusion			х	
criteria			^	
Demographics		Х		
Medical history	Х	х		
Surgery parameters		х		
Adverse events after				
application of pre-		х	x	x
rolled TachoSil®				
Post-operative			x	x
parameters			^	^
Assessment by the				
surgeon (5-Point-			x	x
Likert-Scales)				
Cost-effectiveness				Х

# Demographics:

 Age, gender (if gender is female, pregnancy/breast-feeding (yes/no) should be documented), height, weight

#### Inclusion criteria:

- Inpatient planned for laparoscopic surgery, in the field of gynecology, urology and visceral surgery where pre-rolled TachoSil® was applied and at least 18 years of age

#### Exclusion Criteria:

- Contraindications, such as hypersensitivity to the active pharmaceutical ingredient or to another ingredient of pre-rolled TachoSil®, according to the current SmPC.
- Patient participates in another clinical trial.

# Medical history:

- Concomitant diseases
- Evaluation of haemorrhage risk
- Coagulation status

# Intra-operative parameters:

- Coagulation status
- Diagnosis underlying surgery, including type of surgery (gynecology, urology or visceral surgery)
- Indication for use of pre-rolled TachoSil® (hemostasis, tissue sealing or suture support)
- Description of surgery (Type of minimal-invasive surgical technique, duration)
- Description of TachoSil application (diameter of trocar, dry/wet, localisation, number of pre-rolled TachoSil® applied during surgery, time of compression)
- Primary techniques used for tissue sealing/hemostasis
- Intra-operative adverse events after application of pre-rolled TachoSil®
- Assessment of pre-rolled TachoSil® by the surgeon:
  - ease of use (5-Point-Likert-Scale)
- satisfaction with the application of pre-rolled TachoSil (5-Point-Likert-Scale)

### Post-operative parameters:

- Post-operative adverse events, especially including bleeding and lymph leakage
- length of ICU and overall hospital stay

Overall assessment of pre-rolled TachoSil® by the surgeon:

- overall satisfaction with the application of pre-rolled TachoSil (5-Point-Likert-Scale
- cost-effectiveness, based on subjective assessment of the surgeon, shortening of surgery time and hospital stay.

Adverse events, exposure of a pregnant patient to pre-rolled TachoSil® or pregnancy/breast-feeding after application of pre-rolled TachoSil®, as well as medication error, suspected transmission of an infectious agent and lack of effect.

Informed Consent will be obtained before collection of the first data point.

#### 9 Management and Reporting of Adverse Events

### 9.1 Definitions

#### **Adverse Event**

An adverse event (AE) is any unfavorable and unintended sign (including an abnormal laboratory finding), symptom, or disease temporally associated with the use of a medicinal product, whether or not the event is considered causally related to the use of the product. All AEs (Serious adverse events (SAEs) and adverse events which do not meet the criteria of a SAE), will be recorded and reported in this study. SAEs are defined below in Section 9.2.

### 9.2 Classification

#### **Serious Adverse Events**

A Serious Adverse Event (SAE) is an AE that meets any of the following criteria:

- Is fatal or life threatening, i.e., in the view of the Investigator, places the patient at
  immediate risk of death from the reaction as it occurred. An event would not be
  classified as life threatening solely because, had it occurred in a more serious form, it
  might have caused death. For example, drug-induced hepatitis that resolved without
  evidence of hepatic failure would not be considered life threatening, even though
  drug-induced hepatitis can be fatal.
- Results in persistent or significant disability or incapacity. Disability is defined as a substantial disruption of a person's ability to conduct normal life functions.
- Requires inpatient hospitalization or prolongation of an existing hospitalization.
- Is a congenital anomaly/birth defect.

 Any other important medical event that may not result in death, be life-threatening or require hospitalization, but based upon appropriate medical judgment, may jeopardize the patient and may require medical or surgical intervention to prevent one of the outcomes listed above.

Hospitalization for underlying disease progression will constitute an SAE. Hospitalization for an elective or planned procedure to treat a pre-existing condition is not considered an SAE, unless it results in one of the other outcomes listed above.

